Because it is likely that providers may internalize the best practice metrics once repeatedly exposed to the alert, cluster randomization of patients at the level of the provider will ensure that providers consistently receive an alert or not, which will reduce contamination between study arms. It will also minimize the chance that providers get so accustomed to seeing an alert that they will become less attentive to the condition in patients not generating an alert. We will ask the providers to not discuss the details of the trial and/or alerts amongst each other so as to limit the contamination across study groups. Additional pre- and post- intervention analyses in the control group, leveraging the three-month baseline period, can assess the level of contamination and the effect of secular trends towards better care over time.

Intervention

Providers randomized to the intervention arm will have a best practice alert appear for each of their eligible patients upon opening of the order entry screen in the patient's medical record. This alert informs the provider to the presence of HFrEF, notes the patient's current LVEF and current evidence based medications, and gives access to an order set with recommended evidence- based and FDA- approved therapies for patients with HFrEF. Providers will also have access to a link to best available guideline recommended information regarding treatment of heart failure. With the alerts, we will also make sure to note that monitoring and follow-up are required for prescriptions.

The alert will appear as follows:

Adherence to Evidence Based Therapies in HFrEF

Your patient meets the criteria for having heart failure with reduced Ejection Fraction. Relevant values are listed below:

LVEF

Current Heart Failure Therapies

Beta blocker Carvedilol 3.125mg BID

ACEi/ARB/ARNI Lisinopril 5mg

MRA None

SGLT2-inhibitor None

In order to improve the care of patients with HFrEF, we have included the evidence based medical therapy order set for each of the recommended medications.

OPEN ORDER SET

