This patient is part of a randomized clinical trial. The guideline-recommended treatment for heart failure in the alert is NOT a substitute for clinical judgement and individual-patient-centered decision making. Evidence-based therapies include those that may not be listed here due to patient allergy or contraindication. There are clinical reasons why these recommendations may not apply to your patient. For full treatment guidelines, [click here](#).

Acknowledge Reason for Decision

Below is the order set that will be linked in the alert. It contains evidence-based therapy for HFrEF along with each FDA indication⁹:

9/1/2020 visit with [name], MD for Office Visit

Goal-Directed Medical Therapy for HFref

ACE/ARB/ARNI

▼ Candesartan (Atacand)
FDA-approved for heart failure with reduced ejection fraction, hypertension
 candesartan (ATACAND) 16 mg tablet
Disp-30 tablet, R-2

▼ Captopril (Capoten)
FDA-approved to treat diabetic nephropathy, heart failure, hypertension, myocardial infarction with left ventricular dysfunction
 captopril (CAPOTEN) 12.5 mg tablet
Disp-90 tablet, R-2

▼ Enalapril (Vasotec)
FDA-approved to treat hypertension, symptomatic heart failure.
 enalapril (VASOTEC) 10 mg tablet
Disp-30 tablet, R-2

▼ Lisinopril (zestril)
FDA-approved to treat heart failure with reduced ejection, hypertension, ST-elevation myocardial infarction
 lisinopril (PRINIVL,ZESTRIL) 10 mg tablet
Disp-30 tablet, R-2

▼ Losartan (Cozaar)
FDA-approved to treat hypertension, diabetic proteinuric chronic kidney disease
 losartan (COZAAR) 100 mg tablet
Disp-30 tablet, R-2

▼ Sacubitril-Valsartan (Entresto) 97-103 mg
FDA-approved to reduce the risk of cardiovascular death and hospitalization for patients with chronic heart failure[NYHA II-IV] and reduced ejection fraction
 sacubitril-valsartan (ENTRESTO) 97 mg-103 mg tablet
Disp-60 tablet, R-2

▼ Sacubitril-Valsartan (Entresto) 49-51 mg
FDA-approved to reduce the risk of cardiovascular death and hospitalization for patients with chronic heart failure[NYHA II-IV] and reduced ejection fraction
 sacubitril-valsartan (ENTRESTO) 49 mg-51 mg tablet
Disp-60 tablet, R-2

▼ Sacubitril-Valsartan (Entresto) 24-26 mg
FDA-approved to reduce the risk of cardiovascular death and hospitalization for patients with chronic heart failure[NYHA II-IV] and reduced ejection fraction
 sacubitril-valsartan (ENTRESTO) 24 mg-26 mg tablet
Disp-60 tablet, R-2

▼ Valsartan (Diovan)
FDA-approved to treat hypertension, heart failure.

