 valsartan (DIOVAN)
Disp-30 tablet, R-2

▼ Beta Blockers

▼ Bisoprolol (Zebeta)
FDA-approved for hypertension
 bisoprolol-hydrochlorothiazide (ZIAC) 5-6.25 mg per tablet
Disp-30 tablet, R-2

▼ Carvedilol (Coreg)
FDA-approved to treat hypertension, heart failure with reduced ejection fraction, left ventricular dysfunction following myocardial infarction in clinically stable patients
 carvedilol (COREG)
Disp-60 tablet, R-2

▼ Metoprolol succinate (Toprol-XL)
FDA-approved to treat angina, heart failure with reduced ejection fraction, hypertension, myocardial infarction
 metoprolol succinate (TOPROL-XL)
Disp-30 tablet, R-2

▼ Mineralocorticoid Antagonists (MRA)

▼ eplerenone (Inspira)
FDA-approved to treat hypertension, heart failure after myocardial infarction
 eplerenone (INSPRA) 25 mg tablet
Disp-30 tablet, R-2

▼ spironolactone (Aldactone)
FDA-approved to treat ascites due to cirrhosis, heart failure with reduced ejection fraction, hypertension, primary hyperaldosteronism
 spironolactone (ALDACTONE) 100 mg tablet
Disp-30 tablet, R-2

▼ SGLT-2 Inhibitors

▼ Dapagliflozin (Farxiga)
FDA-approved to treat type 2 diabetes mellitus, heart failure with reduced ejection fraction
 dapagliflozin (FARXIGA) 10 mg tablet
Disp-30 tablet, R-2

▼ Empagliflozin (Jardiance)
FDA-approved to treat type 2 diabetes mellitus
 empagliflozin (JARDIANCE) 10 mg tablet
Disp-30 tablet, R-2

▼ Additional SmartSet Orders

Search
You can search for an order by typing in the header of this section.

Alerts will fire only once per provider, during the first encounter in which a patient is eligible and only when the chart is open to enter orders. This ensures that the alert is displayed at the most relevant places in a provider's workflow and will minimize alert burden. Once a patient is seen by an enrolled provider, they will not generate further alerts, which will ensure that a patient who sees two providers in different arms of the study will not be enrolled twice.

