Should a patient have a documented allergy or contraindication to a particular medication class, this class will not be displayed in the order set for that patient. We will also provide the clinician with the opportunity to dismiss the alert and indicate the reason, including if the patient had any contraindications. Any patient seen by a provider that is randomized to the control study arm will not generate an alert for their provider, but a "silent alert" that registers the patient into the study. Patients will receive care as usual.

Endpoints: The primary outcome for the trial will be the proportion of patients with HfrEF who have an increase in the number of prescribed evidence-based therapies for HfrEF (beta-blockers, ACE-I/ARB/ARNI, MRA, SGLT2i) 30 days post randomization. This endpoint will be based on the prescription of medication rather than filling of the prescription by the patient.

Secondary outcomes will include: percentage of patients prescribed each medication class (i.e. percentage on beta-blockers, percentage on ACE-I/ARB/ARNIs, percentage on SGLT2i, and percentage on MRAs), the percent of filled prescriptions (as assessed by Sure Scripts), medication doses, one-year all-cause mortality, 30-day all-cause hospital admission rate, all-cause 30-day ED visits, and 6 month total healthcare costs. Other data that is present in the EHR that might be related to adverse events such as falls will also be collected. Outcomes will be determined by review of medical, hospital, and billing records.

Secondary analyses will look at outcomes based on insurance coverage, specialty of the provider, and according to prescriptions filled by patients. We will also stratify analyses by provider type (MD vs PA vs NP). Finally, per request of our DSMB, we will collect laboratory values and vital signs as categorical variables to enable simpler detection of safety signals as the data accrues, as well as secondary endpoints at 60 days (to include ED visits, hospitalizations, and all-cause mortality).

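### The bisoprolol entry in the alert's printed order set offers only a bisoprolol-hydrochlorothiazide combination, which adds a thiazide outside the trial's four drug classes

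*Combined protocol and SAP*

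**What the plan says.** The Intervention section prints the alert and then the order set that the provider can open from it. The printed set is introduced with "Below is the order set that will be linked in the alert", so it is presented as the working content of the intervention and not as an illustration. The alert tells the provider that "we have included the evidence based medical therapy order set for each of the recommended medications".

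Under Beta Blockers there are three entries: bisoprolol, carvedilol and metoprolol succinate. The bisoprolol heading names that drug alone, with the brand Zebeta. Its one order line is "bisoprolol-hydrochlorothiazide (ZIAC) 5-6.25 mg per tablet". No single-agent bisoprolol line is printed anywhere in the set.

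The Endpoints section defines the primary outcome through an increase in the number of prescribed "evidence-based therapies for HfrEF (beta-blockers, ACE-I/ARB/ARNI, MRA, SGLT2i) 30 days post randomization", and adds: "This endpoint will be based on the prescription of medication rather than filling of the prescription by the patient".

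The end of the Intervention section describes a filter. If an allergy or contraindication to a medication class is documented, "this class will not be displayed in the order set for that patient". The same paragraph says that a patient of a control-arm provider "will not generate an alert for their provider".

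**The concern.** The heading names one drug and the order beneath it contains two. The second, hydrochlorothiazide, is a thiazide diuretic and belongs to none of the four classes that the trial recommends and counts. A provider who acts on the bisoprolol entry would therefore add a drug that the trial does not set out to promote.

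Two features make this more than a typing matter. The order set is part of what is being tested, so an unintended product in it changes what the alert arm is offered, and only the alert arm. The filter is also described at the level of the medication class. The protocol does not say how combination products are handled, so a contraindication to a thiazide may not hide a line that sits under beta-blockers.

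**Working it through.** The protocol states no figure on this point, so the check is a line-by-line reading of the printed order set against its headings and against the class list in Endpoints.

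**Count of order lines**

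| Block | Order lines | Drug matches heading |
|---|---|---|
| ACE/ARB/ARNI | 9 | 9 |
| Beta blockers | 3 | 2 |
| MRA | 2 | 2 |
| SGLT2 inhibitors | 2 | 2 |
| Total | 9 + 3 + 2 + 2 = 16 | 9 + 2 + 2 + 2 = 15 |

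The one mismatch is bisoprolol. Sacubitril-valsartan is also a combination, but its three headings say so and it falls in the ACE-I/ARB/ARNI class. The eplerenone heading and its order line spell the brand name differently, but the drug is the same.

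**Class membership.** The four classes are beta-blockers, ACE-I/ARB/ARNI, MRA and SGLT2i. Of the two components of the listed product, bisoprolol is in the first and hydrochlorothiazide is in none. No section of the protocol mentions a thiazide as a recommended therapy or explains the combination.

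**Could a line have been lost in the print?** Every one of the 16 headings carries exactly one order line, and the three strengths of sacubitril-valsartan each have their own heading. A missing bisoprolol line is possible but not indicated. Even if one had been lost, the combination would still sit under a heading that does not name it.

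**Who can be exposed.** Control-arm providers see no alert, so exposure through the order set is confined to the alert arm: 655 / 1310 = 50% of planned patients. Within that arm it is limited to patients whose provider opens the order set and selects this line. The documents give no basis for estimating that number.

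**Age of the screen.** It shows a visit on 9/1/2020, and the protocol version is dated 1/31/2022. From 9/1/2020 to 9/1/2021 is 365 days, and from there to 1/31/2022 is 152 days, so the gap is 365 + 152 = 517 days.

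**Effect on the analysis.** The sample size, power and significance level use no input from the order set. The primary outcome counts prescribed classes, and a product containing bisoprolol would presumably count as a beta-blocker, although the protocol does not say how combinations are mapped to classes.

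**The case against.** The strongest reply is that very little follows from this line in practice. Opening the order set is optional. The provider must then prefer bisoprolol to carvedilol or metoprolol succinate, and must select a line that names hydrochlorothiazide in full. The people ordering are physicians, nurse practitioners and physician assistants. The set has a search box for other orders, the alert says that it does not replace the clinician's own judgement, and it can be dismissed with a reason. The Intervention section says the alerts will call for monitoring and follow-up. Endpoints provides for collecting laboratory values and vital signs to detect safety signals, and the data are reviewed for safety at 25% and 50% enrolment. Many patients may already take a beta-blocker, as the example patient in the alert does; for them the entry would be a switch or a duplicate. The Prior and Concomitant Therapy paragraph allows every therapy, so a thiazide breaks no rule. The documents show no harm from this dose, and the filter point is an inference from silence. Finally, the screen is old and the live build may be right.

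Most of this stands, and it is why the point is minor. It does not remove the mismatch. Permission to use any therapy does not make a thiazide one of the recommended ones. Providers who might notice the error are a safeguard, not a reason to leave it in. The age of the screen limits what can be said about the live system, but the January 2022 protocol still presents this set as the one the alert will link to.

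**Conclusion.** The concern holds for the order set as printed. One of 16 order lines, and one of three for beta-blockers, orders a product that its heading does not name and adds a drug outside the four classes. It looks like a slip in building the order set and not a deliberate recommendation.

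Severity is minor. The consequence is a possible unintended co-prescription in the alert arm only. The figure of 655 patients is an upper bound and says nothing about the likely number. No inference about the primary outcome is threatened, on the assumption that the combination is counted as a beta-blocker. Confidence is high about the printed page. Whether the build that providers actually used has the same line cannot be known from the documents.

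**What to change.** Replace the order line under the bisoprolol heading with single-agent bisoprolol, with the clinical team confirming product and strength. Check the live Epic build for the same line and correct it there if it is present. Update the order set printed in the protocol so that the two agree.

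The cost is one order-line change in the build and one in the document. Sample size, analysis and timeline do not change. If the line is found to have been live, a count of how often it was ordered from the set would supply the one number that the documents cannot.

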HIC#2000027014

Pragmatic Trial of Messaging to Providers about Treatment of Heart Failure (PROMPT HF)

NCT 04514458

Protocol and Statistical Analysis Plan

Document Date: 1/31/2022

HRP-503B – BIOMEDICAL RESEARCH PROTOCOL (2020)

Protocol Title: PRagmatic Trial Of Messaging to Providers about Treatment of Heart Failure (PROMPT-HF)

Principal Investigator: [name], MPH, Yale University School of Medicine, Yale New Haven Health System

Co-Investigators: [name], MPH, [name]; F. [name], MHS, Yale University School of Medicine, Yale New Haven Health System

Version Date: 01/31/2022

Clinicaltrials.gov Registration #: NCT04514458

SECTION I: RESEARCH PLAN

[figure not shown]
Statement of Purpose: Heart failure (HF) is the major cause of healthcare expenditure, morbidity, and mortality in the United States.¹ Data from clinical trials suggest that pharmacological therapies prescribed at appropriate doses will lead to dramatic improvements in survival and hospitalization rates in patients with heart failure with reduced ejection fraction (HFrEF). Consequently, major cardiovascular societies assign the highest level of recommendation to use these therapies in all eligible patients.² However, data from several registries over the last three decades has failed to see use of these evidence based therapies at levels noted in clinical trials, despite aggressive guideline recommendations and promotion by thought leaders in the field.³⁻⁵ In fact, our pilot data across the Yale New Haven Health System shows almost identical use of evidence based heart failure therapies as noted in the most current and comprehensive registry—CHAMP-HF.

It remains unclear as to why many patients with HFrEF are not on evidence-based therapies, and why the percentages are consistent across national registries over time. One explanation might be that providers know the data regarding evidence-based therapies, but the therapies only benefit a narrow population. Another factor might be a lack of knowledge among providers about the appropriate management of HFrEF patients. A simple way to test this hypothesis is to examine whether electronic health record (EHR) based "best practice advisories" (BPAs) can increase use of evidence based therapies.⁶ If found to be effective, these low cost interventions can be rapidly applied across large healthcare systems.⁷

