We therefore propose a randomized controlled trial across outpatient clinics at four teaching hospitals within the Yale New Haven Health System comparing the effectiveness of an EHR BPA system that informs practitioners (Physicians, Nurse Practitioners (NPs), Physician Assistants (PAs)) about what medications they can prescribe that are evidence based for HFrEF versus usual care (no alert). The primary outcome for the trial will be the proportion of patients with HFrEF with an increase in evidence based medical therapies for HFrEF(beta-blockers, ACE-I/ARB/ARNI, MRA, SGLT2i (currently at 10%)). Secondary outcomes will include the proportion of patients prescribed each class of evidence-based medication, the percent of filled prescriptions as assessed by Sure Scripts, medication doses, 30-day hospital admission rates, 30-day all-cause ED visits, one year all-cause mortality, and 6 month total healthcare cost. We will also collect other data available in the EHR that may pertain to potential side-effects of the therapies.

Probable Duration of Project: Approximately 3000 unique patient encounters with a diagnosis of HFrEF are generated annually at the proposed sites, with a planned enrollment of 100 unique providers and 1310 patients to start soon after IRB approval, we conservatively estimate that the study will take 2 years to complete.

Background: Heart failure is a complex and heterogeneous disease with mortality and morbidity that rivals most cancers.^{1, 8} There is robust data from clinical trials in support of the premise that pharmacological therapies prescribed at appropriate doses lead to dramatic decreases in mortality and hospitalization rates in patients with HFrEF. As a result, all major cardiovascular societies give the highest level of recommendation to use of these therapies in eligible patients.² However, data from registries and real world analyses shows that use of evidence based therapies falls far short of what is seen in clinical trials. This might be due to the lack of applicability of these practices in the real-world setting. Whether the gap between clinical trial use and real-world practice is due to a lack of knowledge or providers making individualized decisions about their patients is unclear. It is for this reason that we plan to

[figure not shown]
perform the PROMPT-HF Trial across outpatient clinics at four teaching hospitals within the Yale New Haven Health System.

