- Already receiving each of the four classes of evidence-based HFrEF medical therapy

Providers must be practicing at an outpatient cardiology and internal medicine practices within one of the four teaching hospitals within the Yale New Haven Health System and will be selected for study participation based on the frequency with which they see patients who meet the above criteria, based on a retrospective chart review.

How will eligibility be determined, and by whom?

Eligibility of patients will be assessed automatically by the best practice alert framework directly within Epic and will not involve any human intervention. When a provider opens the order entry screen of the patient's medical record, this build will examine the record for all inclusion and exclusion criteria. Those who meet criteria will be immediately and automatically enrolled and placed into a randomization group based on the randomization status of their current provider at the time of enrollment. Providers will be selected as described above via retrospective chart review by study investigators.

Protection of Human Subjects: Protection of Human Subjects: Modifications Made in Response to Findings from the Electronic Alerts for the recently completed Acute Kidney Injury Amelioration (ELAIA-1) trial: The recently completed ELAIA-1 trial was *negative*. Alerts about acute kidney injury (AKI) did not reduce progression, dialysis initiation or death rates among hospitalized patients with AKI. However, there was a small signal for harm at one non-teaching hospital (Lawrence and Memorial Hospital). *Despite* heart failure being an *entirely* different disease state and the intervention being tested in PROMPT-HF is guideline based whereas ELAIA was not, we are making the following modifications to the study out of an abundance of caution. *These have been made in partnership with the leadership at both Yale School of Medicine/Yale Center for Clinical Investigation (YCCI) and Yale New Haven Hospital: Drs. [name] (YCCI), [name] (YCCI), [name] (YNHS), and [name] (YNHS) who believe that studies of decision support tools continue to pose minimal risk to patients.*

The changes are as follows:

- We will restrict the study only to *teaching* hospitals within the YNHS: Yale New Haven, Greenwich, Bridgeport, Hospital of Saint Raphael
- Our Data Safety Monitoring committee will perform an interim analysis of the data at 25% and 50% enrollment

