The primary outcome is the percentage of HFrEF patients on a higher number of evidence-based therapies at 30-days after randomization. Our preliminary data suggests that the baseline rate for increasing evidence-based therapy use after a visit is up to 20%. A clinically meaningful increase from that baseline would be 10%. In a fixed design with no interim analysis, sample sizes of 650 in group 1 and 650 in group 2, which were obtained by sampling 50 clusters with 13 subjects each in group 1 and 50 clusters with 13 subjects each in group 2, achieve 91.207% power to detect a difference between the group proportions of 0.1. After accounting for the 2 interim analyses, the final sample size is 1310. The proportion in group 1 (the treatment group) is assumed to be 0.2 under the null hypothesis and 0.3 under the alternative hypothesis. The proportion in group 2 (the control group) is 0.2. The test statistic used is the two-sided Z-Test (Unpooled). The intracluster correlation is a conservative 0.05, and the significance level of the test is 0.048.

Interim Analysis:

We plan to have interim analyses when 25% (n=328), and 50% (n=655) of patients have been enrolled. The interim analyses will allow us to alter the sample size or stop the trial earlier for ethical considerations, unexpected adverse events, or high efficacy. Earlier stopping will be considered for the reason of safety and efficacy. This is a novel intervention and we are obligated to ensure the safety of the alert and that it is minimal risk. The trial will stop for declaring efficacy if the effect size is large. We will use the O'Brien and Fleming stopping rule to stop the trial earlier if the P value for the primary outcome is 0.00007 for efficacy at 25% enrollment, and 0.005 at 50% enrollment.

Statistical Analysis:

The primary analysis will utilize the intention to treat principle. A generalized linear model will be used to assess the relationship between randomization status and the primary outcome. The model will use a log-link and independent correlation structure to allow for calculation of adjusted risk ratios. Statistical significance will be based on a P value of <0.048 to account for two interim analyses. For categorical secondary outcomes, a similar generalized linear modelling approach will be used. For continuous secondary outcomes, a generalized linear model will be used with an identity-link to describe adjusted absolute differences between outcomes.

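### The four class-specific secondary outcomes count patients already on the class at entry, which dilutes the risk ratio and costs power when prior use is high; a new-start outcome per class avoids this

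*Combined protocol and SAP*

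**What the plan says.** Under Endpoints in Section I, the secondary outcomes include the "percentage of patients prescribed each medication class (i.e. percentage on beta-blockers, percentage on ACE-I/ARB/ARNIs, percentage on SGLT2i, and percentage on MRAs". The Statement of Purpose describes the same outcome as "the proportion of patients prescribed each class of evidence-based medication". Neither place limits the denominator to patients who lack the class at entry, and neither gives a time point.

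The primary outcome, in the same Endpoints section, is a change measure at 30 days: patients who "have an increase in the number of prescribed evidence-based therapies for HfrEF".

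The only exclusion tied to prior therapy is "Already receiving each of the four classes of evidence-based HFrEF medical therapy" (Inclusion/Exclusion Criteria). Patients on one, two or three classes therefore enter. The sample alert under Intervention shows such a patient, on a beta-blocker and an ACE inhibitor but on no MRA or SGLT2 inhibitor.

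On analysis, the Statistical Analysis section says: "For categorical secondary outcomes, a similar generalized linear modelling approach will be used". The primary model it refers to uses a log link and yields adjusted risk ratios, but no covariate is named.

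**The concern.** A patient already on a beta-blocker at the index visit counts as on that class in either arm, and the alert cannot add the class. Such patients contribute equally to the numerators of both arms. They push the ratio of the two percentages toward 1 and add variance unrelated to the alert. The more common the class is at entry, the stronger both effects.

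The class outcomes are where a reader will look to see which prescriptions the alert changed, because the primary outcome shows that something was added but not what. If a real increase in new starts appears as a risk ratio of 1.02 to 1.09 with a wide interval, it will probably be reported as no effect for that class.

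**Working it through.** **Inputs from the documents.** 655 patients per arm (Subject Recruitment). 50 clusters per arm, ICC 0.05, alpha 0.048, two-sided unpooled Z-test (Sample Size Determination). Prior SGLT2i use of 10%: the Statement of Purpose has "SGLT2i (currently at 10" percent, read here as current use.

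**Assumptions.** Prior use of the other three classes is not stated, so 30% to 80% is used as a range. New starts in control are 10% of non-users. There are no stops, and the ICC is the same for every class.

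**The plan's own figure.** With 650 per arm in clusters of 13, the design effect is 1 + 12 × 0.05 = 1.6 and the effective n is 650/1.6 = 406.25. For 0.20 vs 0.30 the unpooled test has power 90.9% at alpha 0.048 and 91.207% at alpha 0.05. The stated 91.207% is therefore reproduced closely enough to use the method below. The documents give no power for the class outcomes.

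**Formulas.** Let b be prior use, s the control start rate among non-users, and k the multiplier under the alert.
- As defined: control b + (1 − b)s; alert b + (1 − b)ks. Mean cluster size is 655/50 = 13.1, the design effect is 1 + 12.1 × 0.05 = 1.605, and the effective n is 655/1.605 = 408.1 per arm.
- New starts among non-users: s vs ks. n = 655(1 − b), cluster size 13.1(1 − b), design effect 1 + (13.1(1 − b) − 1) × 0.05.
- z = difference / sqrt[(p1(1 − p1) + p2(1 − p2)) / effective n]. Power = Φ(z − 1.977) + Φ(−z − 1.977).

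**Worked case, b = 50%, s = 10%, k = 2.**
- As defined: 55% vs 60%, RR 1.09. SE = sqrt[(0.2475 + 0.24)/408.1] = 0.0346, z = 1.45, power 30%.
- New starts: 10% vs 20%, RR 2.0. n = 327.5, design effect 1.2775, effective n 256.4. SE = sqrt[(0.09 + 0.16)/256.4] = 0.0312, z = 3.20, power 89%.

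**Doubling, 10% vs 20% starts among non-users**

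| Prior use | On class, control vs alert | RR | Power as defined | Power, new starts (RR 2.0) |
|---|---|---|---|---|
| 10% | 19% vs 28% | 1.47 | 85.8% | 97% |
| 30% | 37% vs 44% | 1.19 | 52.6% | 95% |
| 50% | 55% vs 60% | 1.09 | 29.8% | 89% |
| 70% | 73% vs 76% | 1.04 | 16.2% | 74% |
| 80% | 82% vs 84% | 1.02 | 11.5% | 59% |

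**1.5-fold, 10% vs 15% starts among non-users**

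| Prior use | On class, control vs alert | RR | Power as defined | Power, new starts (RR 1.5) |
|---|---|---|---|---|
| 10% | 19% vs 23.5% | 1.24 | 34.3% | 55% |
| 50% | 55% vs 57.5% | 1.05 | 10.8% | 40% |
| 70% | 73% vs 74.5% | 1.02 | 7.5% | 28% |
| 80% | 82% vs 83% | 1.01 | 6.4% | 21% |

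The smallest powers count rejections in both directions. Counting only those in favour of the alert lowers them by at most one point (for example 6.4% to 5.5%).

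**Another start-rate assumption.** Sample Size Determination says that "the baseline rate for increasing evidence-based therapy use after a visit is up to 20" percent. If that is split evenly over four classes, 5% of all patients start each class in control. Doubled to 10%, power as defined is 46%, 31%, 30%, 40% and 57% at 10%, 30%, 50%, 70% and 80% prior use, against 79% to 98% for new starts. Here the loss is not steady in b, because a fixed 5% of all patients means a higher start rate among fewer non-users. The new-start outcome is still better at every level.

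**Adjustment instead of restriction.** At b = 50%, removing the between-patient variance due to entry use leaves 0.5 × 0.09 + 0.5 × 0.16 = 0.125. Then SE = sqrt(0.125/408.1) = 0.0175, z = 0.05/0.0175 = 2.86 and power is about 81%, up from 30%. Adjustment on the absolute scale thus recovers most of the lost precision.

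**The case against.** The strongest reply is that the percentage on a class is a legitimate quantity. Prior use is expected to balance between arms. Without stops, the arm difference therefore equals the extra new starts over all patients, which is the effect of the alert on coverage of that class. A class with few non-users has less room to rise, and a smaller effect on coverage there is real. This stands: a reader might infer that the outcome is biased, and it is not. The cost is a diluted ratio and lost precision.

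A reader might also infer that all four outcomes mostly measure prior use. The documents do not show that. They give one class rate, and for the rest they report only "almost identical use of evidence based heart failure therapies as noted in the most current and comprehensive registry", with no figures. For SGLT2i, under 10% vs 20% starts, prior users are 10/19 = 53% of control patients on the class but 10/28 = 36% in the alert arm, and power as defined is already 86%.

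Nor do the documents plan a comparison of risk ratios between classes. Calling such a pattern an artefact would criticise an analysis that the plan does not contain.

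The doubling is larger than the plan's own effect of 20% vs 30%, which is 1.5-fold. With assumed prior use of 80%, 70%, 30% and 10% and independent classes, doubling implies an any-increase rate of (1 − 0.98 × 0.97 × 0.93 × 0.91)/(1 − 0.0168) = 20% in control and (1 − 0.96 × 0.94 × 0.86 × 0.82)/(1 − 0.0168) = 37% under the alert. The 1.5-fold table is therefore closer to the plan. It shows that new starts would often be missed too, though less often than with the outcome as defined.

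Finally, the promised adjusted risk ratios might have been meant to include entry class use. Since no covariate is named, that cannot be assumed.

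**Conclusion.** The point holds as a matter of precision and interpretation for secondary outcomes. As defined, the four class outcomes include prior users and have no named baseline adjustment. At assumed prior use of 50% to 80%, a doubling of new starts shows as a risk ratio of 1.09 to 1.02 and is detected with 30% down to about 11% power, against 89% to 59% for new starts among non-users. At a 1.5-fold effect the outcome as defined has 11% to 6%, against 40% to 21%. At the one documented level, 10% for SGLT2i, the loss is smaller: 86% against 97% for a doubling, and 34% against 55% for a 1.5-fold effect.

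These sizes rest on assumed start rates, assumed prior use for three classes, no stops and one common ICC. The ordering holds in every case computed. The primary outcome already requires an increase and is unaffected.

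A reader might want to add that a change from an ACE inhibitor or ARB to an ARNI registers in no outcome. That follows from the plan's consistent treatment of the three as one class. The three ARNI entries in the order set are strengths of one product. Reporting ARNI separately is optional and not part of this error.

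**What to change.** For each of the four classes, prespecify as the comparative secondary outcome: new prescription of the class by 30 days among patients not prescribed it at the index visit. This also supplies the time point that the present definition lacks. Entry status should be the status recorded before any order is placed at the index visit, so that the subgroup is fixed before the alert can act.

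Report as a companion the percentage still prescribed the class at 30 days among those on it at entry, so that stops are visible. Keep the overall percentage on each class. If that percentage is also compared between arms, name entry use of the class as a covariate in the model.

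The change is to endpoint and analysis wording. The build must read class status to apply the four-class exclusion, and control patients pass the same check through the silent alert. The team should confirm that the status of each class is stored and not only evaluated. The price is one extra line per class and smaller denominators: about 590 per arm at 10% prior use (655 × 0.9), 328 at 50% and 131 at 80%. The power comparison above already allows for this.
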